All MS participants will undergo the following procedures: I. Participants will be asked to refrain from eating for 2 hours prior to their arrival at our center. Once here, after the consenting process is finished, participants will have their temperature taken aurally (two measurements will be taken for reliability) and will then complete a simple motor task, the hand dynamometer test (5 measurements will be taken), an objective measure of physical fatigue that has been used in MS (Greim et al, 2007). They will then have their aural temperature measured again, before filling out questionnaires on fatigue (FSS, VAS), mood (BDI-II), and a diary page. Aural temperature will be recorded once again, just before the pill is administered (placebo or aspirin). II. Scan condition: Participants are then scanned for one hour. Immediately after scanning, aural temperature is recorded, followed by the same set of questionnaires, plus one additional questionnaire, the Global Fatigue Change (GFC). All participants will also be asked which pill they think they received, aspirin or placebo. The hand dynamometer test will be completed once again, followed by a final aural temperature measurement. All of these procedures are expected to take under 2 hours. III. Patients who are not scanned will wait quietly for one hour, and then baseline procedures will be repeated [temperature taken aurally (two measurements will be taken for reliability), repeat the hand dynamometer test, complete questionnaires on fatigue (FSS, VAS)]. Exercise condition: Ten RRMS patients will be randomized in a crossover double-blind study. After undergoing same procedures as above (section I), each subject in the exercise condition will undergo the following additional procedures: subject will have peak ventilatory capacity (Maximum Voluntary Ventilation, MVV) determined before the exercise test via a Vmax Encore System (CareFusion Corp, San Diego, CA). Each subject will have a 5-minute resting phase followed by a three-minute warm up and then a progressive ramped exercise test using a VIA Sprint 150P lower body cycle ergometer (CareFusion Corp, San Diego, CA) until achieving one of the following VO₂max criteria: respiratory exchange ratio (RER) 1.1, increases in ventilation without concomitant increases in VO₂, maximum age predicted heart rate and/or volitional fatigue. An individualized ramping protocol will be used as determined by weight and subject's exercise profile as determined by a certified exercise physiologist. Blood pressure, tympanic temperature, and RPEbr and RPElegs data will be collected at 3-minute intervals. Minute ventilation, expired oxygen (O₂), carbon dioxide (CO₂), watts, RER, and total time will be measured using Vmax Encore Metabolic system (Sensormedics, Inc, Loma Linda, CA). Flow sensor and gas analyzer will be calibrated against known medical grade gases before each test. VO₂max will be determined from peak 20-second average of the breath-by-breath measurement of VO₂. Identical test procedures will be carried out after initiation of placebo or ASA. Anaerobic threshold will be determined for each subject using the V-slope technique. The exercise test will commence one hour after pill was administered. Exercise test: Patients will maintain a cycle cadence between 50-60 revolutions per minute (RPM) on the lower body cycle ergometer for the duration of the test. The test will be terminated when the cadence drops below 40 RPM for 5 seconds, or when participant reaches volitional exhaustion [i.e., in the presence of American Thoracic Society (ATS) standard test termination criteria]. In healthy adults, the estimated time to bring about volitional exhaustion is 8-12 minutes. At termination, RPEbr, RPEleg, blood pressure (BP), and tympanic

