Methods and Statistical approach: Scan condition: All participants will be scanned at New York State Psychiatric Institute at CUMC in consultation with [name] (Co-I, Senior Physicist and Director of physics and engineering), who assisted in MRS analysis of the feasibility data presented here. Aim 1. We will examine the association of brain temperature in centrum semiovale (all neuroanatomical sites were selected consistent with 38) and fatigue (FSS total score) using a partial correlation controlling for sex, age, and depression (BDI-II total score, consistent with 23). Secondary analyses will be conducted using brain temperature in calcarine sulcus and lesion site, and fatigue measured with the MFIS (total score, subscale scores), and VAS of pain, mood, and fatigue. Aim 2. Our primary analysis will determine whether aspirin administration is effective for reducing brain temperature. A 2x2 mixed ANOVA will be run with factors of group (placebo vs. aspirin) and time (Pre vs. Post). Post-hoc tests of all significant effects will be run. A secondary analysis will investigate the impact of aspirin on fatigue. The same 2x2 mixed ANOVA will be run, with VAS of fatigue as the dependent measure. Aim 3: Functional Connectivity analysis. Data preprocessing will be performed with AFNI and the FMRIB Software Library (e.g., 52, 53). A recent fMRI RSFC study identified seven primary brain networks in 979 healthy adults, identifying a central "hub" for each network (component of each network most functionally integrated with the rest of the network).⁵⁴ Guided by the results of this large-scale study, we will place spherical 6-mm radius seed ROIs within the hub of each network. RSFC will thus be derived for each network (consistent with our methods as described in 57). For the full sample (N=20), regressions will be conducted to examine the association of brain temperature and FC within each network. We expect higher brain temperature to be associated with lower FC, particularly in networks previously seen to be impacted by fatigue (e.g., sensorimotor network).⁵⁰ For our analysis of the aspirin subgroup, a 2x2 mixed ANOVA will be run with factors of group and time to identify FC changes from Pre to Post, which we expect in the aspirin group relative to the placebo group. We expect that aspirin (versus placebo) will increase network connectivity from pre- to post-scan. Finally, support our hypothesis that such changes are due to changes in brain temperature, we will investigate whether the degree of change in network efficiency is correlated with degree of brain temperature change within the aspirin group using 3D regression within AFNI. Exercise condition. This is a within-subject, 2 (ASA, placebo) by 2 (Time 1, Time 2) cross-over trial in which each subject will serve as his/her own control. Subjects will be randomized to one of two sequences: the

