
first group will receive ASA at the first exercise session and placebo at the second, while those in group 2 will receive placebo at the first session and ASA at the second. Data analysis will proceed as follows. First, all variables will be inspected for outliers or inconsistent values. Variables that display an extremely right skewed distribution with outliers will be transformed using the log transformation. Any remaining outlier values will be dealt with using winsorization, i.e. the extreme values will be censored down to the nearest non-outlier value. Aim: We hypothesize that participants will demonstrate longer time-to-exhaustion after receiving ASA than after receiving placebo (within-subject crossover design). The measure of interest is the length of time (i.e., time-to-exhaustion) spent exercising at each session. This time has no pre-set upper limit, i.e. patients are free to exercise as long as they wish. This means that the time will not be censored. The effects in a balanced 2x2 crossover trial with treatments A and B with outcome measures YAB and YBA in the two groups, respectively, where A and B are the population means for the direct effects of treatments A and B, respectively, represents a sequence effect, represents a session effect, and A and B represent carryover effects of treatments A and B, respectively. Because ASA has only a short-term effect and the wash-out period is more than adequate, we expect no carryover effects. However, we will still test for carryover effects using the test statistic in Wellek et al. Test for differences between treatment effects: The appropriate test statistic will be an unpaired t statistic on the within-subject differences in outcome between Session 1 and Session 2 (in this order), comparing sequence group AB: $YAB_{1i} - YAB_{2i}$, and sequence group BA: $YBA_{1j} - YBA_{2j}$, over all subjects $i=1, \dots, n_1$ and $j=1, \dots, n_2$. Significance level for the difference will be reported using the probabilities from the t distribution with $n_1 + n_2 - 2$ degrees of freedom. Alternative analysis method: If the observed time measure Y has many outliers and the log transformation is not appropriate, the non-parametric Wilcoxon test will be used in place of the unpaired t-test. Given the pilot nature of this study, we make no power calculations; rather, effect size will be determined from analysis of these preliminary data.

Exempt and Expedited

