Scan condition: 20 RRMS patients will serve in the scan condition. All participants will be asked to refrain from eating 2 hours prior to their scheduled appointment. Participants will be scanned with MRS to derive brain temperature; fatigue will be measured with validated self-report fatigue questionnaires (FSS 46) and body temperature will be measured with an aural thermometer (Braun ThermoScan IRT 4520 Aural thermometer, consistent with our prior studies^{23,24}) immediately prior to scanning. We hypothesize that higher brain temperature in RRMS patients is correlated with worse fatigue. 10 patients will be randomized to aspirin group (standard dose, 650 mg in 1 pill), and 10 patients to placebo (placebo, 650 mg in 1 pill). After being administered aspirin/placebo, patients will have temperature measured aurally and then receive a scan. We hypothesize that brain temperature will decrease in the aspirin group compared to the placebo group. As a secondary outcome, we will examine change in fatigue after aspirin/placebo administration to see whether the aspirin group experienced a greater decrease in fatigue than placebo group. 12 healthy controls will be enrolled to obtain normative brain temperature. These subjects will fill out questionnaires, have temperature taken aurally, and receive a scan. After scanning, aural temperature will be measured and questionnaires filled out. All subjects will receive only 1 scan and only RRMS subjects will be randomized.

All MRIs will be read by study personnel for research purposes, and will also be read by a trained radiologist to screen for the presence of any IFs (incidental findings). If the radiologist sees an IF on a scan, the research team will contact the study subject immediately.

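### VAS fatigue (Aim 2, secondary): replace the 2x2 mixed ANOVA with one ANCOVA on the pre-pill score, and name it as the only treatment test

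*Combined protocol and SAP*

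**What the plan says.** Statistical Procedures, Aim 2, gives the primary analysis, of brain temperature, as "A 2x2 mixed ANOVA will be run with factors of group (placebo vs. aspirin) and time (Pre vs. Post" (the two levels of time). It adds "Post-hoc tests of all significant effects will be run". For the secondary outcome it says "The same 2x2 mixed ANOVA will be run, with VAS of fatigue as the dependent measure". No term of the model is singled out as the treatment test, and no significance level is given for Aim 2.

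The hypothesis stands elsewhere. The Procedures section says "We hypothesize that brain temperature will decrease in the aspirin group compared to the placebo group". There and under Research Question(s)/Hypothesis(es), the fatigue question is whether the fall is larger on aspirin than on placebo.

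A pre-pill fatigue score is collected. The methodology description before Statistical Procedures has patients tested "before filling out questionnaires on fatigue (FSS, VAS), mood (BDI-II), and a diary page", with the pill given after that, and repeats the questionnaires after the scan. Research Question(s)/Hypothesis(es) likewise puts the VAS ratings before the pill and again after the scan.

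On size, Procedures says "10 patients will be randomized to aspirin group (standard dose, 650 mg in 1 pill), and 10 patients to placebo".

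**The concern.** A 2x2 mixed ANOVA gives three F tests, and they answer different questions.

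- **Time** pools both arms, so it picks up any change over the session whether or not aspirin works. It also absorbs half of any drug effect.
- **Group** averages the pre-pill and post-pill values. It carries chance baseline imbalance and only half of any drug effect.
- **Group by time** compares change on aspirin with change on placebo. It is the only treatment test of the three.

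Two things are at stake for VAS fatigue. First, the interaction uses the baseline only by subtracting it in full. Regressing on the baseline lets the data set its weight, and with 10 per arm the difference in precision can matter. Second, the analysis text does not say which term is the result. It directs follow-up of every significant effect, so main effects are not clearly marked as descriptive.

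**Working it through.** **Inputs from the documents.** 10 patients per arm (N = 20), from Procedures and Aim 2. Pre-pill and post-scan VAS fatigue both recorded. The plan has no figure to reproduce: it gives no alpha, SD, effect size or pre-post correlation for Aim 2. The sentence closing the exercise analysis is "Given the pilot nature of this study, we make no power calculations", with the remark that "effect size will be determined from analysis of these preliminary data"; the scan condition has no figures either.

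**Assumptions.** Two-sided 5%; the same SD (sigma) before and after and in both arms; normal data; pre-post correlation rho shown over a range; effect of 1 SD for power.

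**Step 1: the planned treatment test.** In this design the interaction F equals the square of the unpaired t on change, with 18 degrees of freedom. With n = 10 per arm, the variance of the difference in mean change is

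(2/n) x 2 sigma^2 (1 - rho) = 0.4 sigma^2 (1 - rho).

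**Step 2: ANCOVA on the pre-pill value.** The residual variance is sigma^2 (1 - rho^2). Estimating the slope costs a factor (N - 3)/(N - 4) = 17/16. The variance is

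(2/n) x sigma^2 (1 - rho^2) x 17/16 = 0.2 sigma^2 (1 - rho^2) x 17/16.

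**Step 3: ratio.** ANCOVA/change = (1 + rho)/2 x 17/16. The large-sample ratio (1 + rho)/2 would give 0.65, 0.75 and 0.85 at rho 0.3, 0.5 and 0.7, which flatters ANCOVA at this size. The CI-width column also allows for 17 instead of 18 degrees of freedom. Power is from 40,000 simulated trials per setting.

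| rho | Variance, change (sigma^2) | Variance, ANCOVA (sigma^2) | Variance ratio | 95% CI width ratio | Power at 1 SD, change | Power at 1 SD, ANCOVA |
|---|---|---|---|---|---|---|
| 0.3 | 0.280 | 0.193 | 0.69 | 0.84 | 44% | 58% |
| 0.5 | 0.200 | 0.159 | 0.80 | 0.90 | 57% | 66% |
| 0.7 | 0.120 | 0.108 | 0.90 | 0.95 | 78% | 82% |
| 0.8 | 0.080 | 0.077 | 0.96 | 0.98 | not run | not run |
| 0.9 | 0.040 | 0.040 | 1.01 | 1.01 | 99.6% | 99.6% |
| 0.95 | 0.020 | 0.021 | 1.04 | 1.02 | not run | not run |

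Break-even on variance: (1 + rho)/2 x 17/16 = 1 gives rho = 32/17 - 1 = 0.88. On CI width it is about 0.87.

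**Step 4: the main effects.** With no drug effect and no time trend, the chance that at least one of three independent tests is significant is 1 - 0.95^3 = 14.3% (simulated 13.9% to 14.4%). With no drug effect and an assumed 0.5 SD shift in both arms, the time effect is significant in 43%, 56%, 79% and 99.7% of trials at rho 0.3, 0.5, 0.7 and 0.9, while the interaction stays at about 5%. With a true 1 SD drug effect, the group effect has only 20% to 26% power.

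**Step 5: can the same change be made for brain temperature?** The methodology description and Procedures place the scan after the pill, and Procedures allows each subject a single scan. Aims 2 and 3 in Statistical Procedures use pre and post values, and Aim 3 under Research Question(s)/Hypothesis(es) refers to connectivity before and after the pill. Under the first description there is no pre-pill brain temperature, so neither the planned ANOVA nor an ANCOVA on that baseline can be run.

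**The case against.** The strongest reply is that the planned test is sound. In randomized arms the interaction is an unbiased treatment comparison with correct type I error, and the stated hypotheses already point to it. The Aim 3 text reads the same model that way, expecting change in the aspirin arm relative to placebo. Choosing change scores for a secondary outcome of a pilot is not an error. All of this stands. What remains is that precision can be gained almost free, and that the Aim 2 text never names the contrast.

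Three stronger readings are tempting, and the documents do not support them.

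- **That the plan carries a 14% risk of a false aspirin claim.** The 14% is the chance that any of three F tests is significant under the null. The hypotheses imply the group-by-time contrast, which stays at 5% even with a shared time trend. Reporting a time effect as an aspirin effect would be misreporting, which the plan does not propose.
- **That the precision argument covers brain temperature.** The post-hoc sentence is attached to that outcome, but under the one-scan description no pre-pill value exists to adjust for. Nor does the plan specify a mixed ANOVA for aural temperature that could be replaced.
- **That change scores always waste information unless the correlation is perfect.** At N = 20 the advantage ends near 0.88 and reverses slightly beyond it.

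**Conclusion.** The point holds for VAS fatigue as an improvement in efficiency and clarity, not as the correction of an invalid test. Baseline adjustment cuts the variance of the aspirin-placebo difference by about 31%, 20% and 10% at correlations of 0.3, 0.5 and 0.7. It makes no useful difference between about 0.8 and 0.9, and loses about 4% at 0.95. The power figures rest on an assumed 1 SD effect and assumed correlations; the documents support neither a particular value nor a range. The unnamed treatment contrast and the follow-up of every significant effect support the change but would not make a separate finding of inflated error. For brain temperature the conclusion is conditional on resolving how many scans there are and when.

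**What to change.** In Statistical Procedures, Aim 2, replace the sentence on VAS fatigue with wording such as:

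> Post-scan VAS fatigue will be compared between arms by ANCOVA, with treatment arm and pre-pill VAS fatigue as the only terms. The adjusted aspirin minus placebo difference with its 95% CI is the sole treatment test for this outcome. Time and group main effects will be described without tests.

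For brain temperature, first reconcile the number and timing of scans across the methodology description, Procedures, Statistical Procedures and Research Question(s)/Hypothesis(es). If a pre-pill scan exists, use the same ANCOVA. If it does not, specify a between-arm comparison of the post-pill value. Pre-pill aural temperature is then a possible covariate, but its correlation with brain temperature is not given.

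The VAS change costs one degree of freedom (18 to 17), a negligible loss if the correlation turns out very high, and an edit to the text. It needs no new data.

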participants will rate their fatigue, pain, and mood using a visual analogue scale (VAS) and have their body temperature measured again. After the scan is complete, we will repeat these measures. We hypothesize that brain temperature will decrease in the aspirin group compared to the placebo group. As a secondary outcome, we will examine change in fatigue after aspirin/placebo administration to see whether the aspirin group experienced a greater decrease in fatigue than placebo group. Aim 3 investigates fMRI resting-state functional connectivity before and after aspirin/placebo administration. Given fMRI evidence for disrupted neuronal network connectivity in MS patients with fatigue,^{50,51} we will explore the impact of aspirin and expected brain temperature changes on neuronal network efficiency. We hypothesize that (a) aspirin (versus placebo) will increase functional connectivity (which has been linked to greater neural efficiency) within networks previously linked to MS fatigue, and (b) degree of temperature reduction within the aspirin group will be correlated with degree of change in neuronal network efficiency. There has never been a study to experimentally manipulate brain temperature and examine the impact on brain function in any clinical population. Aim 4 investigates aspirin (vs placebo) administered before exercise to increase performance (i.e., increase time to exhaustion). The effect of aspirin before exercise on body temperature will also be examined to determine whether increased time-to-exhaustion is correlated with a smaller increase in body temperature after aspirin compared to placebo.

Scientific Abstract:

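### Aim 3 tests its temperature mechanism by a change-on-change correlation in the 10 aspirin patients only, so nothing shows whether the same correlation arises on placebo

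*Combined protocol and SAP*

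**What the plan says.** In Statistical Procedures, Aim 3 ends with a test meant to "support our hypothesis that such changes are due to changes in brain temperature". It asks whether the change in network efficiency "is correlated with degree of brain temperature change within the aspirin group using 3D regression within AFNI". Hypothesis (b) under Research Question(s)/Hypothesis(es) carries the same restriction: "degree of temperature reduction within the aspirin group will be correlated with degree of change in neuronal network efficiency". The Procedures section gives the arm sizes: "10 patients will be randomized to aspirin group (standard dose, 650 mg in 1 pill), and 10 patients to placebo".

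Two other Aim 3 analyses do use the placebo patients. One is on levels: "For the full sample (N=20), regressions will be conducted to examine the association of brain temperature and FC within each network". The other is on connectivity without temperature: "a 2x2 mixed ANOVA will be run with factors of group and time to identify FC changes from Pre to Post". Aim 2 plans the same group-by-time ANOVA on brain temperature.

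For the change-on-change test there is no placebo correlation, no arm term and no comparison of slopes. Aim 3 states no alpha, precision target or multiplicity rule. The sentence "Given the pilot nature of this study, we make no power calculations" closes the exercise text, and the scan aims have no calculation either.

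**The concern.** Patients were not randomised to their own temperature change. A correlation between two change scores inside one arm is therefore observational, even in a randomised trial. Anything that shifts both measurements between scans, such as motion, drowsiness or time in the scanner, can produce it with no contribution from aspirin.

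The placebo patients are the only data in the plan that could show whether this happens, and this test leaves them out. A positive result could then be read as evidence of a temperature mechanism when the same slope was present on placebo. A null result in 10 patients would say very little.

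**Working it through.** **Inputs.** From the documents: 10 aspirin and 10 placebo patients, and seven networks ("A recent fMRI RSFC study identified seven primary brain networks in 979 healthy adults"). Assumed, because the documents do not give them: two-sided alpha 0.05, true r of 0.5 for illustration, bivariate normality, no dropout. There is no planned figure to reproduce.

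**1. Do both arms have change scores?** The Aim 2 ANOVA on brain temperature and the Aim 3 ANOVA on connectivity are both group by Pre/Post, so they imply both change scores in all 20. Against this, the scan-condition text in Procedures says each subject has one scan, and the study design text places the scan after the pill. The steps below hold only if a pre-pill scan exists.

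**2. The planned test, n = 10.**
- Critical |r| = t/√(t² + df) with df = 8 and t = 2.306: 2.306/√(5.318 + 8) = 0.63.
- 95% CI at an observed r = 0.5: atanh(0.5) = 0.549, SE = 1/√7 = 0.378, so 0.549 ± 0.741, which back-transforms to −0.19 to 0.86.
- Simulated power at r = 0.5 is about 33%. Power reaches 80% only at r of about 0.76 (0.785 by the Fisher approximation).

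**3. All 20 with an arm term and one common slope.**
- df = 17, t = 2.110: 2.110/√(4.452 + 17) = 0.46.
- 95% CI at r = 0.5: SE = 1/√16 = 0.25, so 0.549 ± 0.490, which gives 0.06 to 0.78.
- Simulated power at r = 0.5 is about 62%, if temperature change varies equally in both arms and the slope is shared.

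**4. How far that gain depends on the assumptions.** In the simulation, connectivity change = b × temperature change + unit-variance error, with b = r/√(1 − r²) = 0.5/√0.75 = 0.577 in the aspirin arm.

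| Placebo SD of temperature change ÷ aspirin SD | Placebo slope | Aspirin-only power | Pooled arm-adjusted power | Slope CI narrower by |
|---|---|---|---|---|
| 1.0 | same | 33% | 62% | 35% |
| 0.5 | same | 33% | 44% | 17% |
| 0.25 | same | 33% | 38% | 10% |
| 1.0 | zero | 33% | 20% | not applicable |

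**5. Shared artefact.** Suppose an artefact gives r = 0.5 in both arms, with equal SDs and no aspirin contribution. The aspirin-only test is significant in about 33% of trials and the pooled arm-adjusted slope in about 62%. An arm covariate removes mean differences between arms, not a correlation within them. The slope-by-arm term is significant in only about 5%.

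**6. Power of the slope difference.** With a zero placebo slope and equal SDs, it is about 20% at an aspirin r of 0.5 and 45% at 0.7.

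**7. Pooling without an arm term.** With a 1 SD arm shift in both measures and no true link between them, the false-positive rate is 13.7% instead of 5%.

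**8. Multiplicity.** These are single-test figures. Bonferroni over seven networks raises the n = 10 critical |r| to 0.79. Unadjusted, seven independent tests give 1 − 0.95⁷ = 30% chance of at least one false positive. The planned AFNI regression runs over the image, so it does not reduce to one scalar correlation.

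**The case against.** The strongest reply is that this is a pilot. Aim 3 is framed as exploration, hypothesis (b) asks specifically about treated patients, and the correlation follows the randomised contrasts on temperature and connectivity. All of that stands: a within-aspirin correlation is a legitimate exploratory question and need not be deleted. Pilot status also explains the missing power calculation. It does not explain a causal conclusion drawn without the control data that the plan already implies.

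Three stronger readings are tempting, and the documents do not support them.

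- A reader might infer that Aim 3 discards the placebo arm. It does so in one of three analyses; the N = 20 regression and the group-by-time ANOVA keep it.
- A reader might infer that putting all 20 into one arm-adjusted slope roughly doubles power and supplies the control. The gain needs equal spread of temperature change and a common slope, and the documents give neither. With a zero placebo slope that model loses power. Under a shared artefact it is misled more often than the planned test.
- A reader might infer that the plan lacks between-arm contrasts to back a mechanism. Both are already planned.

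The remedy also has a limit. A placebo slope close to the aspirin slope fits either a shared artefact or a genuine temperature effect present in both arms. It would shift the weight to the randomised contrasts and would not settle the question.

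**Conclusion.** The point holds for the change-on-change test. Its stated purpose is causal attribution, it uses 10 of the 20 randomised scan patients, and nothing in the plan shows whether the correlation appears without aspirin. That gap does not depend on any assumed SD or effect size.

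The imprecision is also real: |r| must exceed 0.63, and power is about 33% at r = 0.5. How much adding placebo patients would help is uncertain. Pooled power runs from 62% down to 38% as the placebo SD falls, and is 20% if the placebo slope is zero. All of these are for one unadjusted test at two-sided 0.05. Even the right comparison, the slope difference, will be imprecise here, so the gain lies in a fairer conclusion more than in a decisive test.

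The scan-count conflict comes first: without a pre-pill scan there are no change scores in either arm. The Lay Abstract, read literally, also randomises only ten of the 20. That wording must be reconciled with the arm sizes in Procedures.

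**What to change.** First reconcile the study design text, the scan-condition procedures, Statistical Procedures and the Aim 3 hypotheses on whether a pre-pill scan is taken. If change scores exist:

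- Fit connectivity change on brain temperature change, arm, and temperature change by arm in all 20 randomised patients. The same model can be used in the AFNI run.
- Report the slope with 95% CI in each arm and the slope difference with 95% CI. Label them exploratory, and do not read a non-significant difference as equal slopes.
- Give the pooled arm-adjusted slope as a secondary estimate only, stating that it assumes a common slope and does not remove a shared artefact. Do not pool without the arm term.
- Change the causal wording of the conclusion to one of association, unless the slope comparison and the already planned between-arm contrasts on temperature and connectivity support more.

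The cost is a little more analysis and a more cautious conclusion. No new patients are needed, and no new scans if the pre-pill scan is confirmed.

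### Exercise times are winsorised before the within-patient differences are taken, with no outlier cut-off or grouping stated, which can distort the crossover contrast

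*Combined protocol and SAP*

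**What the plan says.** The exercise condition is a two-period crossover: "Ten RRMS patients will be randomized in a crossover double-blind study". The outcome is exercise duration: "The measure of interest is the length of time (i.e., time-to-exhaustion) spent exercising at each session".

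The exercise part of Statistical Procedures sets this order of work:

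1. "First, all variables will be inspected for outliers or inconsistent values".
2. Variables with extreme right skew and outliers are log-transformed.
3. Outliers that remain are winsorised: "the extreme values will be censored down to the nearest non-outlier value".
4. Session 1 minus Session 2 differences are compared between the two sequences by an unpaired t-test on n1 + n2 - 2 degrees of freedom. The Wilcoxon test replaces it if there are many outliers and the log is not suitable.

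Of exercise time, which has no pre-set limit, the section also says "This means that the time will not be censored". It makes no power calculation and gives the purpose of the analysis as "effect size will be determined from analysis of these preliminary data". It states no definition of an outlier, no set of values in which outliers are sought, no restriction of winsorising to erroneous values, and no unwinsorised sensitivity analysis.

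**The concern.** Winsorising acts on session times, whereas the test acts on within-patient differences. A fit patient's times can look extreme beside the other nine patients' while that patient's difference is ordinary. Cutting one session time changes the difference; cutting both to the same value sets it to zero.

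The unstated grouping matters as well. Outliers could be sought among all 20 times, within each session, within each treatment, or within each sequence-by-session cell of five. These choices do different kinds of damage, and the plan leaves the choice to be made after the data have been inspected. Time-to-exhaustion is the Aim 4 outcome and the effect size is the pilot's product. With ten patients, altering one of them moves that figure materially.

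**Working it through.** **Plan's own figure.** There is none to reproduce: the plan gives no power, effect size, alpha, outlier cut-off or variance.

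**Inputs from the documents.** Ten patients; two sequences; a t-test on session differences. A 5+5 split is inferred from "The effects in a balanced 2x2 crossover trial with treatments A and B", giving 5 + 5 - 2 = 8 df.

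**Assumed inputs.** Between-patient SD of log time 0.35; within-patient SD 0.10; aspirin/placebo ratio 1.16; two-sided alpha 0.05. Cut-offs of 1.5 IQR and 3 IQR were both run.

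**Why between-patient spread should not matter.** Without winsorising, the SD of a within-patient log difference is 0.10 × √2 = 0.141. The treatment estimate is half the difference in sequence means, so its SE is ½ × 0.141 × √(1/5 + 1/5) = 0.0447. The effect is ln 1.16 = 0.148, and 0.148/0.0447 = 3.3 on 8 df, consistent with the simulated power of about 0.82. The 0.35 does not enter. It does determine which session times look extreme.

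**One patient, invented data set of ten.** A fit patient has 20.0 min on placebo and 23.0 min on aspirin. The unwinsorised trial estimate is 1.18 min.

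- Pooled: both times become 13.1, so the gain goes from 3.0 to 0. The estimate falls by 3.0/10 = 0.30, to 0.88 min.
- By treatment: the times become 11.9 and 13.1, so the gain is 1.2. The estimate falls by 1.8/10 = 0.18, to 1.00 min, yet p drops from 0.0004 to 0.000002 because the spread of the differences has been cut.

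**Simulation, 1.5-IQR rule, no contaminating outliers.**

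| Scale | Grouping | Estimate | Power | Type I error |
|---|---|---|---|---|
| Log | none | unbiased | 0.82 | about 5% |
| Log | pooled | -4% | 0.81 | about 5% |
| Log | by session | -10% | 0.65 | about 5% |
| Log | by treatment | about 0 | 0.77 | about 6% |
| Raw | none | reference | 0.77 | 4-5% |
| Raw | pooled | -9% | 0.77 | about 5% |
| Raw | by session | -16 to -18% | 0.60 | about 5% |
| Raw | by treatment | about -2% | 0.75 | about 7% |

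The rule changed at least one time in 26% to 55% of trials, depending on scale and grouping.

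**Simulation, 3-IQR rule.** On logs, pooled winsorising moves the estimate by about 1% or less and leaves power unchanged; by session, power is 0.79. On raw times by session, power is 0.70 against about 0.78. Type I error by treatment is 0.046-0.057.

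**Wider inputs.** For normal times with an additive effect (between-patient CV from 25%, within-patient CV 3-25%, unwinsorised power 0.79-0.80), the 1.5-IQR rule gave power of 0.61-0.75 by session. Type I error was 0.053-0.077 by treatment and 0.060-0.107 by cell.

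**Rules that cannot fire.** The largest possible z-score in a sample of n is (n - 1)/√n. For n = 5 it is 4/√5 = 1.79, so a 2-SD rule never triggers within a cell. For n = 10 it is 9/√10 = 2.85, so a 3-SD rule never triggers within a session or treatment.

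**The case against.** Four arguments on the other side have weight.

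- **The log step comes first.** Extremely skewed times are logged before winsorising, so raw-scale losses overstate the problem whenever that step is triggered. This stands, and the log-scale figures are therefore the main ones. The by-session loss persists on logs, and moderately skewed times may never be logged.
- **The cut-off is assumed.** The plan names no rule, and a lenient one does little at this sample size. This stands as a limit on the size of the harm. It also shows that the result turns on a choice the plan leaves open.
- **Winsorising guards against aberrant sessions.** With one aberrant short session per trial, winsorising log times raised power from 0.27 to 0.34-0.46. The Wilcoxon test on the differences recovered much of this (0.38-0.40). Pooled winsorising also gained power under heavy raw skew with an additive effect (0.67 to 0.71). It would therefore be wrong to say that no form of winsorising ever helps.
- **This is a pilot with no power claim.** That is true, but the effect size it is meant to supply is the quantity at risk.

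A reader might also infer that the plan contradicts itself by censoring times it says are uncensored. The sentence about censoring follows from the absence of a time limit and mainly concerns survival-type censoring; the other use of the word is a gloss on winsorising. The wording should be tidied, but this is not a substantive conflict. Nor does the plan permit running several analyses and keeping the smallest p-value: it sets a conditional order, though with vague triggers.

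**Conclusion.** The concern holds in a conditional form. The planned order lets one patient's genuine long times be replaced by another patient's value before the contrast is taken, and two unstated choices decide the consequence. Session grouping attenuates the estimate and costs power; pooled grouping attenuates it modestly; treatment grouping mainly inflates type I error. Power loss and inflation can also occur together.

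A reader might conclude that the rule always biases the aspirin effect toward zero. The documents do not support that: they fix no grouping, and under treatment or cell grouping the estimate is essentially unbiased for an additive effect and only 2-6% low for a multiplicative one on raw times.

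All magnitudes rest on the assumed variances, effect, alpha, 5+5 split and cut-off. Confidence is moderate; the change should be made, but the design does not depend on it.

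**What to change.** In the exercise part of Statistical Procedures:

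- Do not winsorise time-to-exhaustion at session level. Correct only verified recording errors, while still blinded to treatment.
- Fix log(time) in advance as the analysis scale. Apply the planned unpaired t-test, with n1 + n2 - 2 df, to the within-patient log differences, and report the aspirin/placebo time ratio with its 95% CI.
- Name the Wilcoxon rank-sum test on the same differences as the single robustness analysis, in place of the present data-dependent switch.
- If a winsorised analysis is kept, make it a sensitivity analysis only, with cut-off and grouping stated. Moving the rule to the differences is not automatically safe: in simulation, type I error was 0.053-0.057 when winsorising across all ten differences, but about 0.15 within each sequence of five.
- Reword the two uses of the term for censoring so that they cannot be read as conflicting.

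The cost is a few sentences, with no new data, patients or procedures. The effect is reported as a ratio rather than in minutes, and the t-test loses some power if a session is truly aberrant, which the rank-sum test partly offsets.
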